9.3.2. Baseline Assessment

Pre-Chronocort® baseline, used in calculations for all change from baseline summaries, will be defined as the latest pre-Chronocort® measurement. This will depend on which feeder study and treatment the subject was receiving immediately prior to entering DIUR-006:

- For subjects entering from study DIUR-003, baseline values are defined as those taken at Visit 1 of this DIUR-006 study, however if a result is missing and there is a suitable result available at the screening visit (taking account of fasting requirements where needed), this will be used in its place.
- For subjects entering immediately from study DIUR-005 who received standard
 glucocorticoid replacement therapy, baseline values are defined as those taken at the last
 visit in the feeder study i.e. Visit 4 (week 24) in study DIUR-005. However, if a result is
 missing and there is a suitable result available (within 14 days prior to the first dose of
 Chronocort® and taking account of fasting requirements where needed), this will be used in
 its place.
- For subjects entering immediately from study DIUR-005 who received Chronocort®, baseline
 values are defined as the pre-Chronocort® values recorded in Visit 1 in study DIUR-005,
 however if a result is missing and there is a suitable result available at the DIUR-005
 screening visit (taking account of fasting requirements where needed), this will be used in its
 place.
- For subjects who delayed entering study DIUR-006 and received standard glucocorticoid therapy in the gap between DIUR-005 and DIUR-006 studies, baseline values are defined as those taken at Visit 1 of this DIUR-006 study, however if a result is missing and there is a suitable result available at the screening visit (taking account of fasting requirements where needed), this will be used in its place.

9.3.3. End of Study Assessment

With commercialisation, some patients may withdraw early from study. This End of Study (EOS) data should be handled in the following way:

Version: 6.0 12 July 2022

 If the EOS visit date falls within the three months immediately following a 6-monthly scheduled visit, then only safety assessments will be performed at the visit. All other subject records should be imputed for EOS by carrying forward the previously collected record to the EOS visit.

• If the EOS visit date is more than three months following a 6-monthly scheduled visit, then a full assessment should be performed at this visit.

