#### 13.1.3 Missing Outcome Data

Blood samples for analysis of 17-OHP and A4 values are to be taken at 09:00 and 13:00, with a window of +/- 1 hour allowed. Missing 17-OHP and A4 values (including those considered missing due to being taken outside the permitted time window) will not be imputed. In calculating the mean of the 09:00 and 13:00 SDS, if one value is missing, then only the non-missing value will be used. If both values are missing, the mean value will be missing.

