9.1. Missing data

Blood samples for analysis of 17-OHP and A4 values are to be taken at the baseline, Week 4, Week 12, Week 24 and 6-monthly visits at both 09:00 and 13:00 hours, with a window of +/- one hour allowed. Missing 17-OHP and A4 values will not be imputed. In calculating the mean of the 09:00 and 13:00 SDS, if one value is missing, then only the non-missing value will be used. If both values are missing, the mean value will be missing.

For subjects based in the US receiving domiciliary visits, only one blood sample for analysis of 17-OHP and A4 will be taken, at either 09:00 or 13:00 hours.

When calculations must be based upon incomplete dates the following process will be used. If year is missing do not impute. The value should be considered missing. If year is populated but both month and day are missing then the date defaults to 1st July. If day only is missing then the day defaults to the 15th of the month.

For adverse events and concomitant medications, the following date imputation methods will be used:

Partial start date

- If the day part is missing then impute as the latest of [1st of the month, date of first dose of Chronocort^{®1}].
- if the month part is missing then impute as the latest of [1st of January, date of first dose of Chronocort^{®1}].
- if the year is missing then do not impute.

Partial end date

- if the day part is missing then impute as the earliest of [last date applicable to the respective month part, date of last study contact or interim data cut-off date].
- If the month part is missing then impute as the earliest of [31st of December, date of last study contact or interim data cut-off date].
- If year part is missing then do not impute.

For definition of treatment emergent and ongoing, if partial dates are only available for start and end, then we are conservative and assume treatment emergent/ongoing.

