9.3.1. Definition of permissible time windows

Actual study day will be calculated by:

• Date of assessment - Date of first dose + 1 (or Date of assessment - Date of first dose if the assessment is before the date of first dose).

Version: 6.0

Protocol No.: DIUR-006

However, due to the first dose being scheduled at 23:00h on the evening of the baseline assessment¹ (Visit 1), a window of +4 hours will be used so that if the time of first dose falls within the window,

the date of first dose will be considered to be the planned date of first dose. For example, if a subject takes their first dose at 01:00h the day after the baseline assessment, the date used for the calculation of study day will still be the day of the baseline assessment.

Vital signs, laboratory data, bone turnover markers, physical examinations (including weight, BMI and waist circumference), endocrine profile (17-OHP and A4), signs and symptoms of adrenal insufficiency, DEXA scans and QoL data will be summarised according to scheduled visit.

Please note that visits 2 and 3 are when specific assessments of 17-OHP, A4 and signs and symptoms of adrenal insufficiency are performed. Any extreme deviations between the actual study day of the scheduled visit and the target study day (see Table 7) will be discussed at the Data Review Meeting. A deviation will be considered extreme if more than +/- 3 weeks (+/- 21 days) from visit 2, +/- 4 weeks (+/- 28 days) from visit 3 and 4, or +/- 3 months (+/- 84 days) for visit 5 and onwards. If 2 or more visits (including unscheduled visits) occur within the same analysis window, then the visit closest to the target study day will be used in the descriptive summaries. In case of equidistant visits to the target study day, then the earliest visit will be used in the analyses. All visits will be displayed in the listings.

Table 7: Target study day for visit assessments

Visit number	Visit description	Target study day	Target study day range
Visit 0	Visit 0/Screening	-14 to -1	
Visit 1	Visit 1/Baseline	1	
Visit 2	Visit 2/Week 4	29	8-50
Visit 3	Visit 3/Week 12	85	57-113
Visit 4	Visit 4/Week 24	169	141-197
6-monthly visits from visit 5 onwards			
Visit 5	Visit 5/Month 12	365	281-449
Visit 6	Visit 6/Month 18	548	464-632
Visit 7	Visit 7/Month 24	730	646-814
Visit 8	Visit 8/Month 30	913	829-997
Visit 9	Visit 9/Month 36	1095	1011-1179

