¹ For subjects entering immediately from the DIUR-005 feeder study this will be the evening of the second day of Visit 4 (Week 24) of the DIUR-005 study.

Protocol No.: DIUR-006

Visit 10	Visit 10/Month 42	1278	1194-1362
Visit 11	Visit 11/Month 48	1460	1376-1544
Visit 12	Visit 12/Month 54	1643	1559-1727
Visit 13	Visit 13/Month 60	1825	1741-1909
Visit 14	Visit 14/Month 66	2008	1924-2092
End of Study/Early Discontinuation	End of Study	Last non-missing assessment within 48 hours of last dose of Chronocort®	

Note: There is no study day 0 as per CDISC standards. Study day 1 is first day of dosing.

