Individual question scores and GFI will be listed.

EQ-5D™

The EQ-5D™ questionnaire consists of two parts, the EQ-5D™ descriptive system and the EQ visual analogue scale (VAS). The descriptive system consists of 5 dimensions: mobility, self-care, usual activities, pain/discomfort and anxiety/depression. The EQ VAS is a visual scale in which the subject gives a single score between 0 and 100.

The results from the dimensions will be combined using a standard method specially designed for the EQ-5D™ questionnaire to give a single index value (EuroQol Research Foundation). Two methods will be used to calculate the single index value:

Method 1 will use the directly elicited 5L value set for the EQ-5D[™] questionnaire as specified in Devlin 2016.

Method 2 will use mapping approach described in van Hout 2012.

A table showing the frequency and percent of subjects with each score for each of the domains will be produced by previous treatment group, visit and feeder study. The denominator for percentage calculations will be based on the number of subjects with an evaluable EQ-5D, at each scheduled visit. A shift table of baseline to end of study will be produced by domain, previous treatment group and feeder study. The denominator for percentage calculations will be based on the number of subjects with an evaluable EQ-5D, at each level of the pre-Chronocort® baseline assessment.

The change from baseline and percentage change from baseline will be calculated for both the single index value calculated from the 5 dimensions and the VAS score. Summary statistics for the absolute values of these two scores as well as change and percentage change from baseline will be tabulated by previous treatment group, visit and feeder study.

Individual question scores for the EQ-5D™ descriptive system, the calculated single index value and EQ VAS score will be listed.

14. Changes from the planned analyses

Due to the COVID-19 pandemic, subjects in the US may receive domiciliary visits to take blood samples for analysis of their 17-OHP and A4 levels. These samples are scheduled to be taken at baseline, Week 4, Week 12, Week 24 and 6-monthly visits at both 09:00 and 13:00 hours, but these domiciliary visits will only occur once daily (with a preference for 09:00 hours). As a result, at the time of finalising the SAP there will unavoidably be missing data from what is due to be collected.

Statistical Analysis Plan

Version: 6.0 12 July 2022

15. References

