Summary of SF-36 percentage change from pre-Chronocort baseline (Full <interim> analysis set)</interim>	14.2.6.1.3	QS209
Summary of GFI score derived from the MAF (Full <interim> analysis set)</interim>	14.2.6.2.1	QS204
Summary of GFI score derived from the MAF change from pre- Chronocort baseline (Full <interim> analysis set)</interim>	14.2.6.2.2	QS205
Summary of GFI score derived from the MAF percentage change from pre-Chronocort baseline (Full <interim> analysis set)</interim>	14.2.6.2.3	QS206
Summary of EQ-5D by domain (Full <interim> analysis set)</interim>	14.2.6.3.1	QS200
Shift table of baseline to end of study for EQ-5D by domain (Full <interim> analysis set)</interim>	14.2.6.3.2	QS210
Summary of EQ-5D absolute values (Full <interim> analysis set)</interim>	14.2.6.3.3	QS201
Summary of EQ-5D change from pre-Chronocort baseline (Full <interim> analysis set)</interim>	14.2.6.3.4	QS202
Summary of EQ-5D percentage change from pre-Chronocort baseline (Full <interim> analysis set)</interim>	14.2.6.3.5	QS203

Statistical Analysis Plan

Version: 6.0 12 July 2022

Protocol No.: DIUR-006

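### SAP 9.3.3 fills the End of Study value by carry-forward while SAP Table 7 restricts it to 48 hours from last dose; the EQ-5D shift table depends on which rule is used

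*SAP*

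**What the plan says.** Three current rules bear on the EOS value.

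- **SAP 9.3.3.** If EOS falls in the three months after a 6-monthly visit, only safety assessments are done. For everything else: "All other subject records should be imputed for EOS by carrying forward the previously collected record to the EOS visit". If EOS is later than that, a full assessment is made.
- **SAP 9.3.1, Table 7.** The End of Study/Early Discontinuation row reads "Last non-missing assessment within 48 hours of last dose of Chronocort".
- **SAP 9.1 and Protocol 13.1.3.** The SAP states "Missing 17-OHP and A4 values will not be imputed". The protocol has the same rule: "Missing 17-OHP and A4 values (including those considered missing due to being taken outside the permitted time window) will not be imputed". Neither makes an exception for EOS.

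One planned output uses EOS by name. SAP 13.5 says of the EQ-5D: "A shift table of baseline to end of study will be produced by domain". SAP 16.1 lists it as Table 14.2.6.3.2, "Shift table of baseline to end of study for EQ-5D by domain". Its percentage denominator is "the number of subjects with an evaluable EQ-5D, at each level of the pre-Chronocort® baseline assessment".

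Protocol Table 1 (note 18) and Protocol 11.1.10 limit a final visit in the same three-month period to collecting adverse events and SAEs, so no EQ-5D is taken there.

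**The concern.** Section 9.3.3 and Table 7 both define the EOS value, and they disagree in the case that 9.3.3 was written for. A subject whose last EQ-5D was weeks before exit has an EOS value under one rule and none under the other. Two programmers could each follow the SAP and produce different counts in Table 14.2.6.3.2. Under 9.3.3 the same answer would also appear twice, once at its own visit and once labelled EOS, with nothing to tell the reader that the second is not a new observation.

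The 9.3.3 rule covers all non-safety records, so on its wording it also takes in 17-OHP and A4, which SAP 9.1 and the protocol say are not imputed.

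**Working it through.** The plan gives no figure for how often 9.3.3 applies, so there is none to reproduce. The check is a comparison of rules, followed by a range under stated assumptions.

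**1. Where the rules part.** Take an illustrative subject with Visit 13 on day 1825 (Table 7 target) and EOS on day 1885, last dose the same day. The gap is 1885 − 1825 = 60 days, inside three months.

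| Rule | EQ-5D value at EOS |
|---|---|
| SAP 9.3.3 | Visit 13 answer, 60 days old |
| SAP Table 7 | none: nothing recorded within 48 hours of last dose |

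If EOS is more than three months after the visit, a full assessment is made and the rules need not differ.

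**2. How often a carried record could satisfy both.** Assume that the last dose is on the EOS date. A carried record then meets the 48-hour limit only if it is at most 2 days old. SAP 9.3.1 equates three months with 84 days (for example, Visit 5: 365 − 281 = 84); a calendar quarter is 365.25/4 = 91.3 days.

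- Uniform timing within the window: 2/84 = 2.4% or 2/91.3 = 2.2% comply, so about 98% do not.
- Exits clustered soon after a visit (exponential timing with scale s, truncated at 91.3 days): (1 − e^(−2/s)) / (1 − e^(−91.3/s)). For s = 7 days this is 24.9%; for s = 14 days, 13.3%. So about 75% to 87% do not comply.

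**3. Share of EOS visits that trigger carry-forward.** Assume that exits are uniform over follow-up. Visits are at Table 7 target days. Table 7 heads its later rows "6-monthly visits from visit 5 onwards", but Week 24 (Visit 4, day 169) might also count, so both are shown. The denominator starts at day 1 or at day 169.

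Full schedule, ending at day 2008:

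| Windows | From day 1, 84 d | From day 1, 91.3 d | From day 169, 84 d | From day 169, 91.3 d |
|---|---|---|---|---|
| Visits 5–13 (9) | 9×84/2008 = 37.6% | 9×91.3/2008 = 40.9% | 9×84/1839 = 41.1% | 9×91.3/1839 = 44.7% |
| Visits 4–13 (10) | 10×84/2008 = 41.8% | 10×91.3/2008 = 45.5% | 10×84/1839 = 45.7% | 10×91.3/1839 = 49.6% |

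Here 1839 = 2008 − 169.

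Latest entrants: 31 October 2018 to 28 February 2022 is 1216 days. Visits 5–9 give 5×84/1216 = 34.5% at the low end. Visits 4–9 give 6×91.3/(1216 − 169) = 52.3% at the high end.

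Over every follow-up length from 1216 to 2008 days:

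- minimum, at 1278 days: 5×84/1278 = 32.9%
- maximum, at 1369 days: (6×91.3 + 91)/(1369 − 169) = 53.2%

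**4. Age of a carried record.** Usually up to 84–91 days. If the preceding visit's record was itself not collected, up to 182.6 + 91.3 = 274 days, about nine months.

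**The case against.** The best defence is that the intent can be read from the SAP. Its revision history shows the EOS row entering the windowing section in version 4.0 and the carry-forward rule in version 5.0, as a deliberate provision for one case. A later, specific rule would naturally govern that case, with Table 7 covering assessments actually made. That may well be the intent. But Table 7's EOS row is also specific to EOS, neither place refers to the other, and SAP section 14 does not mention carry-forward. The stretch of the SAP between 8.2 and 9.1 was not available for review, so the absence of a precedence rule is confirmed only for the text that was.

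Four stronger readings are tempting, and the documents do not support them.

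- *The androgen efficacy results are distorted.* No planned 17-OHP or A4 output names EOS. SAP 9.1 schedules these samples at baseline, Weeks 4, 12 and 24 and the 6-monthly visits, so a short-interval EOS sample can be read as not due rather than missing. The word imputed in 9.3.3, and the unqualified protocol rule, keep the literal conflict alive, but it has an effect only if an EOS row is displayed.
- *The shift-table denominator is undefined.* SAP 13.5 ties it to evaluable subjects at each baseline level, and the natural reading is subjects with an evaluable baseline. At most a clarification is missing.
- *Carry-forward is invalid and must be struck out.* Nothing shows that a last observed value is unusable in a descriptive table. The fault is in labelling it EOS against the SAP's own definition.
- *The affected share is known.* It rests wholly on assumed exit timing. SAP 9.3.3 foresees withdrawals as the product is commercialised but gives no timing.

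**Conclusion.** The contradiction between SAP 9.3.3 and Table 7 is real and should be removed. Its identified reach is one descriptive table on a secondary quality-of-life endpoint, 14.2.6.3.2. There is no hypothesis test on that table, and the by-visit EQ-5D summaries still show each answer at its own visit. Outputs on adverse events, sick-day rules, adrenal crises and laboratory shifts to minimum or maximum do not change.

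Under uniform exits over 1216 to 2008 days of follow-up, roughly one third to one half of EOS visits (32.9% to 53.2%) would fall under the carry-forward rule. With the last dose on the EOS date, about 75% to 98% of those carried records would fail the 48-hour limit, depending on how closely exits follow a visit. These are ranges under assumptions, not estimates from the trial.

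**What to change.** Make SAP 9.3.3, Table 7 and 9.1 consistent:

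- Report observed EOS values under the Table 7 definition, with N. In Table 14.2.6.3.2, add a category for no EOS assessment and confirm that the denominator is subjects with an evaluable baseline.
- If a last value is wanted for every subject, show it separately, labelled as last observed on treatment and flagged in tables and listings, with its actual study day.
- State that 17-OHP and A4 are not carried forward, in line with SAP 9.1 and Protocol 13.1.3.
- Align the undefined safety assessments in 9.3.3 with the adverse-event and SAE collection in Protocol Table 1 (note 18) and 11.1.10. This also settles whether laboratory tests, vital signs and weight could be read as records to carry forward.

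A single sentence giving 9.3.3 precedence would end the contradiction, but it would leave older answers labelled as EOS.

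The cost is SAP wording and one table shell, with no change to data collection. The observed EOS N becomes smaller, by up to about one third to one half under the timing assumptions above.

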9.4. Handling outliers

Any extreme values which are considered to have potential to impact the interpretation of results will be discussed at the Data Review Meeting (see Section 4.1) and sensitivity analyses may be performed as required.

10. Study population

10.1. Disposition of subjects

Subject disposition, including subjects from the feeder studies who don't meet the inclusion/exclusion criteria for DIUR-006, will be listed and summarised by overall DIUR-006 study, feeder study, previous treatment and will include reason for withdrawal from DIUR-006. For subjects who withdraw due to pregnancy an extra row will be included to show the number who re-entered the study.

10.2. Protocol deviations

Any deviations from the protocol will be reviewed at the Data Review Meeting but prior to database lock. Each protocol deviation will be classified as either 'minor' (unlikely to affect trial outcomes) or 'major' (likely to affect outcomes). Subjects with major protocol deviations will not lead to exclusion from the full analysis set. In addition, protocol deviations will be grouped into the following high-level categories:

- Inclusion criteria subject failed to meet all inclusion criteria,
- Exclusion criteria subject met at least one exclusion criteria,
- Study procedure site or subject did not follow procedures specified in protocol,
- Titration site or subject deviated from the titration process,
- Treatment Chronocort® not taken as per protocol,
- NIMP subject used an unauthorised Non Investigational Medicinal Product,
- Drug Accountability subject or site failed to account for all Investigation Medicinal Product,
- Safety Reporting site or subject did not follow safety reporting procedures,
- Informed Consent site or subject did not correctly document informed consent,
- Other any other protocol deviations not fitting into the categories outlined above.

Protocol deviations will be listed and summarised by overall DIUR-006 study, feeder study, previous treatment, by classification (major or minor) and protocol deviation category. The listing will also show whether protocol deviations were related to COVID-19 or not. Additionally, a separate summary of COVID-19 related protocol deviations will be produced.

10.3. Demographic and baseline characteristics

For subjects from the DIUR-003 feeder study, demographic data, medical history and any current medical conditions will be collected at the baseline visit of this DIUR-006 study. For subjects from DIUR-005, demography data collected at the start of the DIUR-005 feeder study will be used, with any changes that occurred during or after the feeder study and prior to entry into DIUR-006 being noted.

The following demographic and baseline characteristics will be summarised and listed: age (calculated in whole years), gender, race, height, weight, BMI, waist circumference and body surface area.

Baseline disease characteristics including time since CAH diagnosis, whether the subject was hospitalised in the last year due to CAH, the number of adrenal crises in the past year and prior CAH medications will be summarised and detailed listings will be produced.

Congenital adrenal hyperplasia medical history, other medical history excluding CAH related events and prior medications will each be summarised, and detailed listings will be produced.

10.3.1. Disruptions due to COVID-19 pandemic

Disruptions due to the COVID-19 pandemic will be summarised by feeder study and previous treatment. The summary will include an overview of study visit or study medication disruptions due to the COVID-19 pandemic, as well as including whether the scheduled visit was delayed or scheduled assessments were not done. Detailed listings of study visit disruptions and study medication disruptions will be produced.

10.4. Treatment compliance

For treatment compliance to Chronocort®, the study will be split into the following interval:

• Overall: The overall period will start from the first dose taken in the evening of visit 1 up to the morning dose of the last planned 6-monthly visit prior to the data cut-off).

Compliance will be calculated as a percentage for each subject, for the interval by

$$\frac{\text{actual total dose}}{\text{expected total dose}} \times 100.$$

The actual total dose for each interval will be calculated by subtracting the number and dose of capsules returned at the next visit from the number and dose of capsules dispensed. The actual total dose for the overall period will be a summation of the actual total dose over all visits.

Actual total dose and expected total dose will only be calculated where a subject has the opportunity to return capsules prior to the data cut off. If the subject is dispensed capsules but hasn't yet had the opportunity to return capsules they will be excluded from the calculation of subject compliance.

Summary statistics will be produced for the overall subject compliance, by feeder study and previous treatment. A listing of subject compliance (including flags for when this is <80% or >120%) and Chronocort® drug accountability will also be produced.

Use of "sick day" medication will be considered separately to compliance to Chronocort® (see Section 11.3.1).

Version: 6.0 12 July 2022

11. Primary safety analyses

